11. STATISTICAL ANALYSIS PLAN

1. Statistical Analysis Plan Summary

Study Design

The study is a pilot study to look at the safety of concurrent PD-1 inhibitor and SRS for relapsed/refractory myeloma. A total of 24 patients will be enrolled on the trial (20 is the minimum, with an additional 4 patients, to make for any attrition and/or loss to follow-up). 12 patients will be allowed to not have measurable myeloma disease in this trial. Once 10 patients are enrolled, we will stop trial for 3 months to assess for acute toxicity, and then resume the trial. The estimated exact Clopper-Pearson 95% confidence interval for a 20% rate based on 5 responses in 20 patients is (0.087, 0.491), with a precision of 0.185. If we see lower than 20% difference in rate of toxicity at 3 months, the combination will be deemed safe.

A minimum of 20 patients are required to complete full treatments. An additional 20% is allowed for drop out/failure to adhere to required follow-up and treatment recommendations. Thus, 24 patients will be allowed to be enrolled on the trial to make for any attrition and/or loss to follow-up. 12 patients will be allowed to not have measurable myeloma disease.

# of Responses / # of Patients	95% confidence interval
5 / 20	(0.087, 0.491)
6 / 24	(0.098, 0.467)

Populations for analysis

- Enrolled set: All subjects who signed an informed consent.
- Safety set: All subjects who received at least one dose of any study drug.
- Full analysis set: All subjects from the safety set who have the required follow-up and treatment adherence to evaluate response and safety over time.

2. Statistical Analyses

1. Response

IMWG criteria will be used to assess response. Proportion of patients achieving stable

disease or better will be reported at **6 months** and **12 months**; Response rates will be reported along with 95% confidence intervals will be estimated using the Clopper-Pearson method.

2. Safety

Proportion of acute (at **3 months**) and late toxicity (**6 and 12 months**) will be reported, and 95% confidence intervals will be estimated using the Clopper-Pearson method.

3. Overall Survival

For overall survival, death from any cause will be defined as the event. Patients will be censored at time of last follow-up. OS will be estimated using the Kaplan-Meier product-limit method. Overall survival will be analyzed at **6 months, and 12 months**.

4. Biological variables

Descriptive statistics for the frequency and absolute cell counts for the major lymphocyte populations (CD3, CD4, CD8, CD19) T cells and monocytes (CD14) along with other markers listed above will be estimated.

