Baseline work-up (per NCCN guideline) within 28 days +/- 14 days prior to enrollment: CBC with Diff, CMP, Calcium, Albumin, Serum Protein analysis, Quantitative Immunoglobulin, Serum Immunofixation (SIFE), 24 hr urine total protein, Urine Immunofixation, Serum Free Light Chain, Bone Marrow Biopsy (with IHC, flow, cytogenetics, FISH),

Whole Body PET/CT, Biopsy of Osseous or extra-osseous site (only if clinically indicated);
Pregnancy test;

Inclusion Criteria:

- 1) ≥ 18 years old; ISS stage I-III multiple myeloma that has progressive, relapsed, or refractory disease;
- 2) Able to give informed consent;
- 3) ECOG 0-1;
- 4) Relapsed and/or refractory myeloma; There is no minimum or maximum number of previous therapies that a patient may have received previously before being put on the current trial.
- 5) ≥ 1 osseous and/or extra-osseous lesion that can be radiated;
- 6) Candidate for pembrolizumab (as determined by physician, and adequate organ function as noted in **Table 1**);
- 7) Candidate for radiotherapy (as determined by treatment physician); These patients can have symptomatic disease and/or asymptomatic disease. A minimum of one site of radiation is required to any osseous and/or any extra-osseous disease. Radiation to any bony parts of the Head and Neck, Skull, Spine, ribs, and/or extremities are allowed. Radiation to any bony part for documented lytic disease is allowed. Radiation to any soft tissue plasmacytoma (including osseous and extra-osseous plasmacytoma) is allowed. The only exclusion criteria for radiation, is CNS metastases (see exclusion criteria # 16);
- 8) Measurable myeloma disease (**urine protein > 200 mg in 24 hr urine collection, serum free light chain ratio > 100 with an abnormal k/l ratio, serum M protein > 0.5 g/dl**) ; **12 of the 24 patients do not have to have measurable disease;**
- 9) Negative urine pregnancy test within 2 weeks for female subjects;

Female subjects of childbearing potential should have a negative urine or serum pregnancy within 72 hours prior to receiving the first dose of study medication. If the urine test is positive or cannot be confirmed as negative, a serum pregnancy test will be required.

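### The SAP's only precision table is labelled for responses in 20 or 24 patients, but the enrolment rule guarantees only 12 patients with measurable disease for the IMWG response rate

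*Combined protocol and SAP*

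**What the plan says.** The Study Design text of Section 11 sets the sample size: "A total of 24 patients will be enrolled on the trial (20 is the minimum, with an additional 4 patients" cover attrition. It supports this with a Clopper-Pearson interval, described as that for a "20% rate based on 5 responses in 20 patients is (0.087, 0.491), with a precision of 0.185". The small table below it is headed "of Responses / # of Patients" and has two rows: 5/20 with (0.087, 0.491) and 6/24 with (0.098, 0.467). No other precision figure appears in the plan.

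The same text says that "12 patients will be allowed to not have measurable myeloma disease in this trial". Inclusion criterion 8 in Section 2 agrees: "12 of the 24 patients do not have to have measurable disease". The Protocol Summary, the enrolment paragraph of Section 10 and Appendix VI repeat the allowance. Criterion 8 defines measurable disease by paraprotein limits: "urine protein > 200 mg in 24 hr urine collection, serum free light chain ratio > 100 with an abnormal k/l ratio", and a serum M protein above 0.5 g/dl.

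On analysis, Section 11 says "IMWG criteria will be used to assess response" and plans to report the proportion with stable disease or better at 6 and 12 months, with Clopper-Pearson intervals. Section 3 words the endpoint differently, as the number of patients with any IMWG response from baseline. The full analysis set requires follow-up and treatment adherence. It does not require measurable disease, and nothing in Section 11 says how patients without it enter the response rate.

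**The concern.** Read by its heading, the table tells the reader how precisely a response rate will be known, and it does so with every enrolled or evaluable patient in the denominator. Up to half of the 24 may have no paraprotein above the protocol's own limits at entry. The myeloma labs scheduled in Sections 2 and 9 follow those same paraproteins.

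If these patients are left out of the response analysis, the interval rests on a smaller sample than any the table shows. If they are kept in, the denominator matches the table, but the rate mixes patients with and without a measurable baseline. Section 4 says the study should inform later trial designs on early safety and efficacy, so a response rate with an unstated denominator and an unsupported precision could be carried forward.

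**Working it through.** **Inputs.** From Section 11: 24 patients planned, 20 minimum, 12 allowed without measurable disease, two-sided 95% Clopper-Pearson intervals. The illustrative rate is the table's own: 5/20 = 6/24 = 25%.

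**Formula.** For x events in n patients, the lower limit is the 0.025 quantile of Beta(x, n − x + 1) and the upper limit is the 0.975 quantile of Beta(x + 1, n − x). Half-width = (upper − lower)/2.

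**Step 1: reproduce the plan.**
- 5/20: (0.0866, 0.4910). Half-width (0.4910 − 0.0866)/2 = 0.202.
- 6/24: (0.0977, 0.4671). Half-width (0.4671 − 0.0977)/2 = 0.185.

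Both printed intervals reproduce to three decimals. The sentence around them does not:
- 5/20 is 25%, not 20%. A 20% rate would be 4/20, with (0.057, 0.437) and half-width 0.190.
- The precision of 0.185 attached to 5/20 is the half-width for 6/24.

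**Step 2: patients guaranteed to have measurable disease.** With 24 enrolled and the allowance fully used, 24 − 12 = 12. If the four allowed losses all fall among them, 12 − 4 = 8.

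**Step 3: precision at the same 25% rate.**

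| Responders / patients | Exact 95% interval | Half-width |
|---|---|---|
| 6/24 | (0.098, 0.467) | 0.185 |
| 5/20 | (0.087, 0.491) | 0.202 |
| 3/12 | (0.055, 0.572) | 0.258 |
| 2/8 (worst case) | (0.032, 0.651) | 0.310 |

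With 12 patients, the half-width is 0.258/0.202 = 1.28 times that for 5/20 and 0.258/0.185 = 1.40 times that for 6/24 (ratios from unrounded limits).

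**Step 4: other rates with 12 patients.** From 2 to 10 responders, the half-width runs from 0.232 to 0.289, above both 0.202 and 0.185. At 1 or 11 it is 0.191, and at 0 or 12 it is 0.132. At matched rates, 12 patients always give the wider interval. At 50%, the half-widths are 0.289 (6/12), 0.228 (10/20) and 0.209 (12/24). At 0%, they are 0.132, 0.084 and 0.071.

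**The case against.** **The table was probably meant for toxicity.** The 5/20 sentence sits between the pause after 10 patients for acute toxicity and the 20% safety rule, and 20% is the toxicity goal in Section 2. No response rate of 20% or 25% is hypothesised anywhere. This stands. On that reading the denominators are right, the wording and heading are wrong, and the response rate has no precision statement at all. The correction needed in Section 11 is the same.

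**The documents do not say that these patients cannot be scored.** This also stands. The criterion 8 limits are thresholds, and a value below a threshold is not zero. Every patient must have a lesion that can be irradiated, PET/CT is planned every three months, and PET/CT change is itself a secondary endpoint. Appendix IV gives the IMWG criteria only as a link. Against this, the flow chart footnote makes PET/CT depend on insurance approval, and follow-up marrow is done only if clinically indicated. Scorability is therefore neither ruled out nor assured.

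**Stronger readings that the documents do not support.**
- A reader might infer that keeping all 24 in the denominator would halve a 25% rate to 3/24 = 12.5%. That needs none of the 12 to count, under Section 3's any-response wording. Under Section 11's stable disease or better, patients who merely do not progress could count. The opposite extreme is (3 + 12)/24 = 62.5%. The direction of the bias is not fixed.
- A reader might compare 8 patients with the 0.185 printed for the trial. That sets a sample after losses against one before losses. Like for like, 8 against 20 is 0.310/0.202, about 53% wider, and only in the worst case.
- A reader might conclude that 12 patients can never reach the printed precision. At 0/12 or 12/12 the half-width is 0.132, so this is too absolute.

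**Response is secondary in a pilot.** True. It limits the importance of the point but does not justify a label that attaches the wrong sample size to the response rate.

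**Conclusion.** The point holds as a mislabelled precision statement together with an undefined response denominator. The heading attaches to response a precision based on 20 or 24 patients, while the enrolment rule guarantees 12 with measurable disease. At the table's 25% rate, the response half-width is then 0.258, about 28% wider than for 5/20 and 40% wider than for 6/24.

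This rests on two assumptions. The first is that the full allowance of 12 is used; with fewer such patients the loss is smaller. The second is that patients without measurable disease are not reliably scorable for IMWG response. The documents leave that open.

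The primary toxicity endpoint is not affected by measurable disease, and the printed intervals themselves are correct. A reader might infer that the trial is too small or that its enrolment rule is wrong; nothing here supports that. The matter should be corrected before analysis, but it does not threaten the primary result.

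**What to change.** In Section 11:

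1. Relabel the 5/20 and 6/24 rows as precision for the toxicity rate.
2. Correct the sentence above the table: 5/20 is 25%, with half-width 0.202; 0.185 is the half-width for 6/24.
3. State that the main IMWG response rate and its Clopper-Pearson interval use patients with measurable disease at baseline, and that the all-patient rate is supportive.
4. Add a response row: 3/12, (0.055, 0.572), half-width 0.26. Optionally add 2/8, (0.032, 0.651), half-width 0.31, labelled as the worst case if all four losses fall among patients with measurable disease.

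The cost is a few lines of SAP text. The downside is that the stated precision for response becomes less favourable. Enrolment and procedures do not change.

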1. PROTOCOL SUMMARY

Abbreviated Title	Pilot Study of Pembrolizumab and Single-fraction, Low-dose, Radiation Therapy in Patients with Relapsed or Refractory Multiple Myeloma
Trial Phase	Pilot Study
Clinical Indication	Relapsed or Refractory Multiple Myeloma
Trial Type	Pilot study
Type of control	None
Route of administration	Patients will receive on day 1, cycle 1 , radiotherapy (8 Gy/1fx) to an extra-osseous or osseous myeloma site followed by pembrolizumab (200 mg/kg i.v. on day 2 or 3 , then every 3 weeks +/- 7 days).
Trial Blinding	N/A
Number of trial subjects	24 patients (20 patients minimum, with 4 extra patients to account for loss to follow-up/attrition and/or failure to comply with recommended treatments); 12 patients will be allowed to not have measurable myeloma disease.
Estimated enrollment period	2 years
Description of enrollment	Following evaluation by medical oncology and radiation oncology, patients will be enrolled. Baseline assessment prior to enrollment may include bone marrow biopsy, peripheral blood collection, and staging of the patient per standard of care. Baseline serum and urine paraprotein analysis, bone marrow biopsy, PET/CT imaging, routine blood work, and baseline physical exam prior to enrollment. Patient with measurable myeloma disease will be screened for tolerability to Pembrolizumab and radiotherapy. Patients will be assessed at 1st month and every 3 month for response using the standard International Myeloma Working Group (IMWG) Response Criteria, and will undergo routine myeloma labs every 6 weeks until progression or as clinically indicated ; Patients with stable disease or better per IMWG response criteria will continue with maintenance pembrolizumab (200 mg/kg every 3 weeks for 2 yrs) . Patients that have progressive disease, or relapse after a complete response will be removed from the trial and treated per standard of care at the discretion of the treating physician.
Duration of Intervention	At least 24 months of Pembrolizumab, or until progression.
Duration of Evaluation	3 year (2 yrs for accrual, and at least 1 year follow-up for the last patient accrued on the study)
Estimated duration of trial	3 years (2 years to accrue + 1 years to follow all patients)
Duration of Participation	3 years
Study Center	Emory University. Atlanta, Georgia.

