9. TRIAL FLOW CHART

9.1 Study Flow Chart (Table 4: Trial Flow Chart)

Procedure	Pre- Treatment (within 28 days of starting)	Cycle 1, Day 1 week 1	Cycle 1, Day 2-3	Cycle 2, Day 22	q 3 WK cycles	q6 WK cycles x 2 yr or until progression	q 3 months (Rad Onc)	q 6 months
Initial Screening	X							
Informed Consent	X							
Inclusion/Exclusion	X							
Prior and Concomitant Medication	X							
Full Physical Examination	X			X				
Review of Systems	X			X		X	X	X
Vital Signs	X	X		X		X	X	X
Weight	X	X		X		X	X	X
ECOG Performance Status	X	X		X		X	X	X
HBcAb, HepC Ab	X							
*Bone Marrow Biopsy	X							X (clinical indication)
PET/CT	X						X	
Adverse effects Assessment	X			X	X (Pembro)	X	X	X
Labs								
Baseline Labs *	X							
Myeloma Labs *, LDH, ESR				X		X		
T3, FT4, TSH	X						X	
Pregnancy Test- urine or ser	X						X	
Urinanalysis	X						X	
uric acid, mg, phos, Coags (PTT,	X							
Correlative Biomarkers								
Serum markers (collect)	X	X (pre-RT)	X (Pre-PD1)	X (pre-PD1)		X (3,6 mo) (Pre-PD1)		
ExtraOssseous/Ossseous Biopsy* (clinical indication)								
Treatment								
*Pembrolizumab 200 mg IV			X	X	X			
RT (8 Gy/1fx)		X						
Survival Analysis								X
IMWG Assessment*	X						X	
CTCAE Toxicity*					X	X		

* EOS = end of study (at progression, or when patient stops being treated on the trial)

* Pembrolizumab 200 mg IV q3wk should be given for at least 2 yr and/or until progression.

* Baseline labs = CBC with Diff, CMP, calcium, Albumin, Serum Protein analysis, Quantitative Immunoglobulin, Serum Immunofixation (SIFE), 24 hr urine total protein, Urine Immune-Fixation, Serum Free Light Chain;

*Bone Marrow Biopsy (with IHC, flow, cytogenetics, FISH);

*Whole Body PET/CT every 3 months (as long as insurance approves);

*Biopsy of Osseous or extra-osseous site (if clinically indicated at baseline);

*Myeloma labs: (CBC with diff, CMP, Calcium, Quantitative Immunoglobulin, M-Protein (serum and Urine), Serum Free Light Chain;

* IMWG Assessment = Done at least during 1st month and every 3 months, or as clinically indicated;

*CTCAE Toxicity at the radiated site once at 3 months, 6 months, and 12 months;

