Absolute Neutrophil Count	Carbon Dioxide ‡	results are noted	Free thyroxine (T4)
Absolute Lymphocyte Count	(CO_2 or bicarbonate)	Urine pregnancy test †	Thyroid stimulating hormone (TSH)
	Uric Acid		PK
	Calcium		
	Chloride		Blood for correlative studies
	Glucose		
 • see biomarkers section 10.1 • The additional blood that is collected will be sent to [name] lab for this analysis
	Phosphorus		
	Potassium		
	Sodium		
	Magnesium		
	Total Bilirubin		
	Direct Bilirubin (If total bilirubin is elevated above the upper limit of normal)		
	Total protein		
	Blood Urea Nitrogen		

† Perform on women of childbearing potential only. If urine pregnancy results cannot be confirmed as negative, a serum pregnancy test will be required.

‡ If considered standard of care in your region.

Laboratory tests for screening or entry into the Second Course Phase should be performed within **14 days +/- 7 days** prior to the first dose of treatment. After Cycle 1, pre-dose laboratory procedures can be conducted up to 7 days prior to dosing. Results must be reviewed by the investigator or qualified designee and found to be acceptable prior to each dose of trial treatment.

Withdrawal/Discontinuation

When a subject discontinues/withdraws prior to trial completion, all applicable activities scheduled for the final trial visit should be performed at the time of discontinuation. Any adverse events which are present at the time of discontinuation/withdrawal should be followed in accordance with the safety requirements. Subjects who a) attain a CR or b) complete at least 24 months of treatment with pembrolizumab may stop taking the drug and discontinue the trial, at the discretion of the treating physician. After discontinuing treatment following assessment of CR, these subjects should return to the site for a Safety Follow-up Visit and then proceed to the Follow-Up Period of the study.

Blinding/Unblinding

Not Applicable, as this is an open pilot study.

Visit Requirements

Visit requirements are outlined in Section 8.0 - Trial Flow Chart. Specific procedure-related details are provided above in Section 9.0 - Trial Procedures.

Screening

The screening period will be 28 days from enrollment.

Enrollment and Treatment Period

Enrollment period to accrue all 24 patients will be over two years. 12 patients will be allowed to not have measurable myeloma disease.

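### The 10-patient safety pause is timed from enrolment, which the documents define in two ways, so accrual can reopen before the last of the 10 patients reach their 3-month toxicity assessment

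*Combined protocol and SAP*

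**What the plan says.** Section 3 (Primary Objective) and Section 11 (Study Design) give the same rule: "Once 10 patients are enrolled, we will stop trial for 3 months to assess for acute toxicity, and then resume the trial". Neither place requires that the 10 patients have been treated, or have completed the 3-month assessment, before the trial resumes.

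The primary endpoint in Section 3 is CTCAE toxicity above grade 2 at the irradiated site at 3 months. The starting point of those 3 months is not stated there. Section 8 (Radiation Toxicity Evaluation) times the toxicity visits from completion of radiotherapy.

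On what enrolment is, some places point to consent, with screening afterwards:
- Section 11, populations: "Enrolled set: All subjects who signed an informed consent". Treated patients are a separate set: "Safety set: All subjects who received at least one dose of any study drug".
- Section 10, Screening: "The screening period will be 28 days from enrollment".
- Section 9.1, flow chart: consent and eligibility sit in the column "Pre- Treatment (within 28 days of starting").

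Other places put evaluation and work-up first:
- Section 1: "Following evaluation by medical oncology and radiation oncology, patients will be enrolled".
- Section 2, Trial Schema: "Baseline work-up (per NCCN guideline) within 28 days +/- 14 days prior to enrollment". The Trial Overview in Section 2 has the same order.

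**The concern.** A pause held to assess a 3-month endpoint should end when the patients concerned have reached that endpoint. This one ends on a calendar date counted from an earlier event. A patient who enrols on one day and is irradiated some days later is still short of 3 months, by that number of days, when accrual reopens.

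With only 10 patients in the look, one or two missing assessments are 10% to 20% of the information. If enrolment is also taken as consent, a patient who fails screening and is never irradiated could fill one of the 10 places, and the look would rest on fewer treated patients than it appears to.

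**Working it through.** The pause is a rule without a derivation, so there is no figure of the plan's to reproduce.

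**Inputs.** Pause: 3 months, about 3 × 30.4 = 91 days (Sections 3 and 11). Longest lag from consent to treatment: 28 days (Sections 9.1 and 10). Accrual: 24 patients in 2 years (Sections 1 and 10), which is 24/24 = 1.0 per month, or 24/21 = 1.14 per month if three of the months are paused. The mean spacing is then 30.4 or 26.6 days.

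**Step 1: the 10th patient.** Let day 0 be the 10th enrolment and L the days from enrolment to radiotherapy. Accrual reopens on day 91. The 3-month point falls on day L + 91. Time since radiotherapy at reopening is 91 − L, and the shortfall is L.

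| L (days) | Days past radiotherapy at reopening | Shortfall (days) |
|---|---|---|
| 0 | 91 | 0 |
| 7 | 84 | 7 |
| 14 | 77 | 14 |
| 28 | 63 | 28 |

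On the consent reading L lies between 0 and 28. On the other reading L is not given. Section 8 places CT simulation several days before radiotherapy, so I assume 0 to 7 days. Even at L = 0 there is no time for a late visit or for data review.

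**Step 2: how many of the 10 are short.** A patient enrolled t days before the 10th is short if that patient's own lag exceeds t.
- Even spacing, all lags 28 days: the 9th patient is at 91.3 + 30.4 − 28 = 93.7 days (not short) at 1.0 per month, and at 91.3 + 26.6 − 28 = 89.9 days (short) at 1.14 per month. So 1 or 2 of the 10 are short.
- Random (Poisson) arrivals, 100,000 simulated trials per setting: the mean number short is about 1.5 if lags are spread evenly over 0 to 28 days, and about 2.0 if all are 28 days. The chance that two or more are short runs from 37% to 65%. As a check at 1.0 per month with all lags 28 days: mean 1 + 28/30.4 = 1.92, and chance of two or more 1 − exp(−28/30.4) = 0.60.
- Enrolment after screening, lags spread evenly over 0 to 7 days: the mean is about 1.1, and the chance of two or more is 11% to 12%.

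**Step 3: new patients in the gap.** Over the longest gap of 28 days, 28/30.4 = 0.9 to 28/26.6 = 1.1 patients would enrol, so about one.

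**Step 4: screen failures (consent reading only).** The documents give no rate; I assume 10% to 30%.
- Treated among 10 consented: 10 × 0.9 = 9 down to 10 × 0.7 = 7.
- Chance of at least one screen failure: 1 − 0.9^10 = 0.65 to 1 − 0.7^10 = 0.97.
- Chance of seeing any event at a true 20% rate: 1 − 0.8^10 = 0.893 with 10 patients, 1 − 0.8^7 = 0.790 with 7.
- Upper exact 95% limit with no events: 1 − 0.025^(1/10) = 0.308 with 10, 1 − 0.025^(1/7) = 0.410 with 7.
- If the 24 also counted consents: 24 × 0.7 = 16.8 to 24 × 0.9 = 21.6 treated, against a minimum of 20.

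**The case against.** The best defence is that the consent reading rests on the label of an analysis set, not on a definition of the accrual event. Section 1 enrols patients after evaluation. Inclusion criterion 8 in Section 2 applies a measurable-disease rule to 12 of the 24, which suggests that the 24 are eligible patients. The spare places ("20 patients minimum, with 4 extra patients to account for loss to follow-up/attrition") are for losses among patients already on study. This stands in part: the Section 11 label, the Section 10 screening sentence and the flow chart point the other way, so the text does not settle the matter.

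Second, if the lags are equal, a patient who consents at reopening is not irradiated before the 10th patient reaches 3 months. With L the same for both, the new patient's radiotherapy falls on day 91 + L or later, and the 10th patient's 3-month point is also day 91 + L. Early exposure needs a new patient who is screened faster. That is correct and limits the harm, but the decision to reopen is still taken without the full data.

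Third, other safety information exists: the 1-month radiation visit (Section 8), adverse-event assessment at pembrolizumab cycles (Section 9.1), the early-termination criteria (Section 7) and committee review (Section 13). Patients are not unmonitored. None of these, however, is a planned look at the 3-month endpoint in the first 10 patients.

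Fourth, the sentence says that the pause is for assessing toxicity, so a sensible team would finish the assessment first. Probably so, but the text sets a length rather than a completion condition.

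**Conclusion.** The pause does not secure its own purpose. This holds under either meaning of enrolment whenever radiotherapy comes after it. The size is modest. On the consent reading the shortfall is 0 to 28 days for the 10th patient, about 1 to 2 of the 10 are short at the planned accrual, and screen failures could count. On the other reading the shortfall is an unstated lag, about one patient is affected, and screen failures do not count.

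A reader might infer more, and the documents do not support it:
- That enrolment simply means signed consent. Sections 1 and 2 contradict this.
- That the pause is 28 to 42 days short. 28 days is the maximum, and the extra 14 days come from the response-visit window in Section 2. No window is stated for the 3-month toxicity visit.
- That all 14 remaining patients would be exposed on incomplete data. At 1.0 to 1.14 patients per month, about one could enrol during the gap.
- That only 7 to 9 of the 10, or 17 to 22 of the 24, would be treated. These figures need both the consent reading and an assumed screen-failure rate.

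The absence of a toxicity count that would prevent resumption is a separate matter, not argued here.

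**What to change.** In Sections 3 and 11:
- Trigger the accrual pause when the 10th patient has started combination treatment, meaning day-1 radiotherapy and the first pembrolizumab dose. The endpoint concerns the combination, so radiotherapy alone should not count.
- Reopen accrual only when all 10 have completed the 3-month irradiated-site toxicity assessment, or their non-evaluable status is documented. Report how many were assessed.
- State that the 3 months of the primary endpoint run from radiotherapy, if that is intended.

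Throughout the document:
- Use one definition of enrolment. Reconcile Sections 1, 2, 9.1 and 10 with the analysis-set label in Section 11.
- State whether the 20 and the 24 count treated patients.
- The sponsor should clarify whether stopping the trial means accrual only, and how patients who have consented but not started treatment when the pause begins are handled.

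The cost is a few sentences and no added procedures. Counted from the 10th consent, the pause would last 91 to 119 days instead of 91, so up to about 4 weeks longer, plus any delay from late visits. If consents are now being counted, replacing screen failures among the 10 would also take time.
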